7 INTRODUCTION

7.1 STUDY RATIONALE

The aim of this randomized controlled trial (RCT) is to assess the impact of using virtual reality therapy in pain management outcomes – including pain intensity and pain interference levels, back pain function, sleep disturbance, anxiety, depression, behavioral skills development, health outcomes and satisfaction in a cohort of participants with chronic pain of the lower back.

7.2 BACKGROUND

Chronic pain is one of the most common reasons adults seek medical care¹: chronic pain affects between 50 and 116 million Americans, more so than cancer, diabetes, and cardiovascular disease combined¹⁻⁴. Other estimates suggest that up to 40% of American adults suffer from chronic pain, ranging from mild to severe⁵. Pain treatment and management are traditionally based around utilizing pharmacological management tools, which typically involve opioids. Although some non-opioid pharmaceuticals and non-pharmacological therapies are becoming available, there is still a significant unmet need for integrative, easily accessible, non-opioid solutions for chronic pain.

Approximately 25 million American adults are living with moderate to severe chronic pain (i.e., pain scoring 4-7 on a Visual Analog Scale and lasting over 3 months) that limits their activities and diminishes their quality of life^{6,7}. Close to 85% of these participants do not find meaningful relief from current non-opioid treatments (i.e., they do not experience a long-term $\geq 50\%$ reduction in their pain levels)⁸.

Opioids are commonly prescribed for pain treatment and management. These agents can yield both inconsistent and sub-optimal results⁹ and greatly increase the risk of the participant developing an opioid addiction or Opioid Use Disorder (OUD). Data from the U.S. Centers for Disease Control (CDC) revealed that even a single day of opioid therapy can predict up to a 6% increase in the risk of the participant developing a dependency within a year¹⁰.

To reduce addiction and provide relief for the millions of chronic pain sufferers, new low-risk, non-opioid pain analgesics are needed. On-demand digital therapeutics may provide home-based access to pain education and skills-based pain self-management. Particularly during the COVID-19 pandemic, home-based behavioral pain care has gained interest, importance, and engagement among participants. Home-based digital pain treatment options include those involving therapist instruction, as well as fully automated behavioral programs. For the latter, the portfolio of self-treatment options includes computer applications for symptom tracking, education, and treatment; web-based programs that include self-paced multisession skills-based pain management learning modules; and virtual reality (VR) immersive treatment¹¹.

7.3 DEVICE DESCRIPTION

7.3.1 INDICATIONS FOR USE

EaseVRx is an investigational, prescription-use immersive virtual reality system intended to provide adjunctive treatment based on cognitive behavioral therapy skills and other evidence-based behavioral methods for participants (age 18 and older) with a diagnosis of chronic lower back-pain (defined as moderate to severe pain lasting longer than three months). The device is intended for in-home use for the reduction of pain and pain interference associated with chronic lower back pain.

7.3.2 SYSTEM DESCRIPTION AND COMPONENTS

EaseVRx is an investigational medical device with preloaded software content on a proprietary hardware platform that delivers cognitive behavioral skills training and other behavioral methods to participants diagnosed with chronic pain. It is an immersive VR system that delivers the VR content while incorporating biopsychosocial pain education, diaphragmatic breathing training, mindfulness exercises, relaxation exercises, and executive functioning games. The medical device integrates an all-in-one head-mounted display with a Software Application and a Breathing Amplifier™ to enable the diaphragmatic breathing exercises. The device is intended to be self-administered, unsupervised in the participant's home while the participant is in a seated position. The device is powered by a rechargeable lithium battery. Each device is intended for a single participant. The medical device is meant for repeated use.

There are two main components of the EaseVRx system, as follows.

Head-Mounted Display (HMD)

The all-in-one mounted display consists of an off-the-shelf VR headset, modified with a Breathing Amplifier™ accessory (See Figure 1 below). The headset is a standalone VR system comprised of the following:

- Adjustable straps to allow the user to comfortably use the headset
- Mounted high resolution display
- Positional audio speaker system
- Buttons to power on/off, control volume, and navigate content
- Integrated microphone for use with some content
- Breathing Amplifier™ modification to direct breath toward microphone

A Breathing Amplifier™ is added to the headset by the Sponsor, AppliedVR, Inc., hereafter AppliedVR. This mechanical attachment is designed to enhance the user's engagement in certain content by amplifying the user's exhalation into the on-board microphone input to generate a visualization of the user's breath within the VR content.

Front View

[figure not shown]

Figure 1: (Left): EaseVRx Headset

(Right): Drawing depicting buttons and their locations

[figure not shown]

Figure 2: Breathing Amplifier™ Component of EaseVRx

Head-Mounted Display (HMD) Off-the-shelf Software

HMD off-the-shelf software comprises of the following:

- **General operating system:** off-the-shelf operating system modified by AppliedVR to support and execute the functions of EaseVRx
- **Bootloader:** off-the-shelf firmware component that turns on the HMD and verifies that critical software components for operation are present and activated
- **Perceptual User Interface (PUI):** off-the-shelf component that acts as a user interface “wrapper” around the general operating system
- **System ROM:** off-the-shelf general computing component that contains the necessary software and firmware for the device image, and drivers to handle HMD specific functions such as buttons, light sensors, and lens display

7.3.3 APPLIEDVR SOFTWARE FOR EASEVRX

The EaseVRx software is designed to provide cognitive behavioral therapy (CBT) and other behavioral methods within an immersive VR environment. EaseVRx software is installed on a general operating HMD system. The breathing shield component of EaseVRx acts as a mechanical amplifier enabling the software to visualize the exhalation.

EaseVRx runs on an off-the shelf general computing operating system, Android, that was modified by AppliedVR to support EaseVRx's delivery of cognitive behavioral therapy, hereby referred to as "content." Users receive EaseVRx pre-installed with all necessary content. EaseVRx does not require any participant information in order to initiate treatment, nor is there anything for a participant to install. Upon receiving the device, a participant only needs to power the device on and follow the instructions on the display to initiate sessions.

7.4 STUDY INTERVENTIONS

The study intervention will include evidence-based digital devices that offer non- pharmacological solutions to managing pain.

Skills-Based VR (EaseVRx)

Participants allocated to the two EaseVRx arms will use a multi-modal, skills-based, self-management VR program, called EaseVRx (AppliedVR; Los Angeles, CA), that incorporates the evidence-based principles of CBT and mindful meditation. EaseVRx combines biopsychosocial education, pain education, breathing training, relaxation exercises, and executive functioning games to provide a mind-body approach toward living better with chronic pain. The standardized, reproducible, 56-day program delivers a combination of skills training and CBT-related treatments through scheduled daily virtual experiences. Each VR experience lasts between 2-16 minutes, with an average duration of 6 minutes. The VR treatment modules are designed to minimize triggers of emotional distress or cybersickness. For the proposed study, participants in the skills-based VR arm will be instructed to complete the full 56-day treatment using a Pico G2 4K VR headset. There are 5 types of modules, as follows:

- **Interoceptive modules:** an entirely new and powerful element added to the treatment program to help understand and perceive what is going on inside the body, and to provide a biofeedback-like platform in which the changes in the observed environment reflect a progressively enhanced state of relaxation.
- **Education modules:** helps the user understand why the VR exercises are relevant to their pain as well as specific topics often used in pain psychology treatments. They learn about the neurobiology of pain, the role of mood and stress in pain, pain catastrophizing, activity pacing and goal setting. The goal is for the user to create self-management steps and a toolkit of strategies they can use to manage their response to pain.
- **360-degree video modules:** high quality 360-degree videos with voiceovers, music, breathing effects, and sound effects are designed to maximize relaxation and engagement of participants.
- **Game modules:** games are designed to maximize distraction and engagement, increasing the cognitive load on participants, and decreasing their perception of pain.

- **Dynamic breathing modules:** based on evidence-based biofeedback training designed to enhance awareness of one's physiological response to pain and to self-regulate that response. In a virtual world, the user experiences a gamified biofeedback session where they are introduced to awareness of their breath via visualization in the virtual environment in the form of air bubbles. In multiple sessions, the user receives increasingly challenging tasks to practice diaphragmatic breathing while interacting with the virtual environment. The user is also asked to pace their breath according to an expanding and contracting ring in the environment to slow their breath and create physiological changes associated with relaxation. The user's exhale is measured by the microphone embedded in the Pico G2 hardware, offering biodata-enabled immersive therapeutics.

Sham VR

In an ongoing systematic literature review using Cochrane criteria, few VR studies have been found that adequately blind participants to the treatment procedure. VR-CORE guidelines suggest using an active control in VR clinical trials and promote the use of non-immersive, 2D content within a VR headset as an optimal control. Thus, participants in the Sham VR group will receive the same Pico G2 4K headset as participants in the immersive VR groups, but rather than view 360-degree, 3D, interactive content specially selected for efficacy, they will only have access to 2D nature footage with neutral music layered on top that is selected to be neither overly relaxing nor distracting. The experience of Sham VR is similar to watching a large-screen TV, but it is not interactive. The advantage of Sham VR is that it controls for the novelty and immersion of the hardware and isolates the effect of VR skill-based training.

7.5 DOSING AND ADMINISTRATION

Weeks 1-8:

All participants will receive a VR headset and will be instructed to use VR once a day for 8 weeks.

Weeks 9-16:

For the 2 groups that are assigned to the arms with an extended 56-day on-demand period, participants will have the option of accessing VR for an additional 8-week period at their discretion. These groups will be instructed to use VR on an as-needed basis (i.e., there will be no set requirement for daily use as with the initial 8-week treatment phase).

7.6 TECHNICAL SUPPORT

Participants in both arms will receive remote technical support from the research and operations team. The idea is that issuing devices is usually insufficient to achieve behavior change; supporting those devices with high-touch yet scalable care is a vital component.

Participants will be provided with device use instructions as well as emails describing the study details. Instructional videos will be made available to participants, and access to remote technical support will be provided.

Participants will receive a telephone number, email, and will have access to contact support staff as needed. The Research support staff will also reach out if there is a lack of survey completion.

7.7 RISK/BENEFIT ASSESSMENT

7.7.1 KNOWN POTENTIAL RISKS

Short-term risks associated with the study may include minor psychological distress from questionnaires regarding health, and small risk of VR-related “cybersickness,” which involves transient symptoms related to entering VR environments (vertigo, nausea, headache). Risks for cybersickness are mitigated by the design of the VR programs in this study. Previous research with this program demonstrates that less than 10% of participants reported cybersickness that prevented them from using Virtual Reality 11, ¹². There are no anticipated long-term risks from participating in this study.

7.7.2 KNOWN POTENTIAL BENEFITS

Potential immediate benefits include reduction of pain due to chronic low back pain (CLBP) and global improvements in psychological health. Potential long-term benefits include improved functionality, development of behavioral coping skills, reduced opioid use, and improved global physical health.

7.7.3 ASSESSMENT OF POTENTIAL RISKS AND BENEFITS

Virtual reality hardware and software have advanced significantly in the past several years and sophisticated motion tracking helps to minimize discomfort among participants. Modern studies utilizing VR have found high satisfaction with devices among participants. Participation in the study may alleviate pain among individuals who have previously relied on opioids, subsequently decreasing both opioid-induced side effects and providing pain relief. Sustained pain relief may allow individuals to return to work faster, improve physical mobility, and enhance biopsychosocial health. We believe the short- and long-term anticipated benefits outweigh minimal short-term risks. Furthermore, risks of cybersickness and discomfort will be assessed following 1 week of usage and will be monitored closely.

To minimize the risk of breaches in confidentiality associated with survey collection, study staff will be assigned unique passwords and usernames to access secure servers. Additionally, identifiable information for participants will be obfuscated using unique ID numbers and a linking list will be held in a secure location.

8 STUDY OBJECTIVES AND ENDPOINTS

AIMS/OBJECTIVES	ENDPOINTS	JUSTIFICATION FOR ENDPOINTS
PRIMARY AIM		
Primary Endpoint: Assess the impact of skill-based VR on pain Intensity or Interference compared to sham VR. 
Assess effect of EaseVRx vs. Sham VR on group	The primary endpoint in this study is a significant change in pain intensity or pain inference at the end of the 8-week treatment period among individuals in the two skills-based VR arms compared	The Brief Pain Inventory (BPI) survey is a validated instrument with excellent content validity, construct validity, and reliability in participants with chronic pain.

score change from baseline to end of treatment on pain intensity
 
 Assess effect of EaseVRx vs. Sham VR on group score change from baseline to end of treatment on pain interference 	
to those in the two Sham VR arms.
 
The outcome measure used to quantify this endpoint is the BPI survey.
 
Interference and intensity are tested separately, and therefore, two (2) multiplicity adjusted statistics are produced. Study success will be declared if statistical significance is demonstrated on at least one of the endpoints.
 
The primary endpoint will pool the two EaseVRx stratum (EaseVRx) together and the two Sham stratum (Sham VR) together.
 
The outcome measure is administered before the 8-week intervention, during and immediately upon completion of the 8-week intervention via the Curebase dashboard.
	
Widely used and therefore may be expected by some reviewers.

---	--	---

SECONDARY AIMs


Secondary Aim #1: Assess effect of EaseVRx vs. Sham VR by comparing:
 
 Percentage of participants with a $\geq 30\%$ change in pain intensity measured with the BPI from pre-treatment to end-of-treatment (8 weeks) for each group Percentage of participants with a $\geq 30\%$ change in pain interference measured with the BPI (as represented by a single composite score derived from 7 pain interference questions) from pre-treatment to 	
The first secondary endpoint is the group level comparison of the percentage of participants in each arm that experience a clinically significant change in pain intensity or pain interference respectively.
 
The outcome measure used to quantify this endpoint is the BPI survey.
 
Clinical significance for this endpoint is defined as a 30% change from baseline.
 
Interference and Intensity are tested separately, and therefore, two (2) multiplicity adjusted statistics are produced. Study success will be declared if statistical significance is
	
The BPI survey is a validated instrument with excellent content validity, construct validity, and reliability in participants with chronic pain.
 
The study is powered to accomplish secondary endpoints which require statistical power beyond what is required for the primary endpoint alone.
 
Therefore, the trial may demonstrate a difference between groups that is small and not necessarily meaningful.
 
The secondary endpoint using this responder definition will accompany the primary results to help interpret the primary results.

--	---	---

end-of-treatment (8 weeks) for each group
	
demonstrated on at least one of the endpoints.
 
The outcome measure is administered before the intervention, during and immediately upon completion of the 8-week intervention via the Curebase dashboard.
	
See the Statistical Analysis Plan for additional details.


Secondary Aim #2: Assess the effect of EaseVRx vs. Sham VR by comparing:
 
 • Change in Oswestry Disability Index (ODI-2.1b), PROMIS Sleep Disturbance, PROMIS Depression and PROMIS Anxiety from pre-treatment to end-of-treatment (8 weeks) for each group 	
The secondary endpoints are clinically significant changes in Oswestry Disability Index (ODI-2.1b) results, PROMIS Sleep Disturbance scores, PROMIS Depression scores and PROMIS Anxiety scores from pre-treatment to end-of-treatment (8 weeks) for each group.
 
Outcome measures used for this endpoint include the BPI survey, Oswestry Disability Index (ODI-2.1b) results, PROMIS Sleep Disturbance scores, PROMIS Depression scores and PROMIS Anxiety scores.
 
The outcome measures are administered before the intervention and immediately upon completion of the 8-week intervention via the Curebase dashboard.
	
The ODI, and PROMIS Sleep Disturbance, Depression and Anxiety surveys are all validated instruments with excellent content validity, construct validity, and reliability in participants with chronic pain.

Secondary Aim #3: Assess effect of EaseVRx vs. Sham VR by comparing participant satisfaction at end-of-treatment (8 weeks) for each group.
	
The third secondary endpoint compares participant satisfaction at the end of treatment across the EaseVRx and Sham groups.
 
The outcome measure used to quantify this endpoint is a custom survey developed by the AVR research team to assess participant satisfaction.
 
This outcome will be collected immediately upon completion
	
The AVR participant Satisfaction survey was developed internally by the Research team to assess satisfaction with the EaseVRx and Sham treatments.

	of the 8-week intervention via the Curebase dashboard.	
EXPLORATORY AIMS		
Exploratory Aim #1: Assess the impact of skill-based VR in follow-up pain adjusting for baseline pain. This endpoint is included to primary sensitivity around the primary endpoint.	
Continuous group difference in follow-up scores adjusted for baseline.
 
Interference and Intensity are tested separately, and therefore, two (2) multiplicity adjusted statistics are produced.
 
The outcome measure used to quantify this endpoint is the BPI survey.
	
Included to enable understanding potential limitations in the primary endpoint.
 
The variables are inclusion criterion, and therefore regression to the mean could be important.
 
Deals with floor and ceiling effects of the change score.
 
Does not require the pre- and post-values to be linearly related.

Exploratory Aim #2: Assess the impact of skill-based VR based on clinical importance changes in a responder framework. This endpoint is included to provide sensitivity around the secondary endpoint.	
Clinically Important Difference (CID) in Interference/Severity
 
Brief Pain Interference Scale (score range 0-10); CID = 2
 
Brief Severity Item (score range 0-10); CID = 2
 
Interference and Intensity are tested separately, and therefore, two (2) multiplicity adjusted statistics are produced.
	
Commonly CID thresholds are commonly used to answer the question of whether statistically significant differences in groups are driven by meaningful improvements for individuals.
 
Both 30% change and CID thresholds are used in responder analyses. By including both, the research team will answer the question of whether the study would have obtained a different result using one versus the other.
 
See the Statistical Analysis Plan for additional details.

Exploratory Aim #3: Assess the impact of skill-based VR on changes in healthcare utilization and outcomes throughout an 8-week intervention and follow-up period.	
Pain-related healthcare utilization will be assessed in a subset of participants for whom access to complete insurance claims files are available. All claims for medical care associated with CLBP will be included and includes claims for the following types of services:
	
While the EaseVRx intervention targets pain and pain interference, it should follow that pain-related medical resource use should be reduced with clinical improvement. Healthcare resource use is difficult to track and assign to a particular diagnosis. Linking the participants to their own claim

	
 • Number and type of imaging and diagnostic procedures • Number and type of health care practitioner visits including specialty care • Number of chiropractic and physical therapy visits • Number and type of emergency room visits • Number and type of surgeries • Number, type, and duration of hospitalizations • Frequency of 30-, 60-, 90-day readmissions • Complications that can be assigned to the pain or pain-related interventions 	records to allow for assessment of changes over time.
Exploratory Aim #4: Assess effect of EaseVRx vs. Sham VR by comparing change in participant's Global Impression of Change (PGIC), Concerns About Pain (CAP-6); and behavioral skills from pre-treatment to end-of-treatment for each group.	
The exploratory endpoints are clinically significant changes in PGIC, CAP and behavioral skills from pre-treatment to end-of-treatment (8 weeks) for each group.
 
Outcome measures for this endpoint include the PGIC, CAP-6 and a behavioral skills survey developed by the AVR team.
	
The CAP-6 survey is a validated instrument with excellent content validity, construct validity, and reliability. The behavioral skills survey has not been validated but has been found informative for internal use.

Exploratory Aim #5: Assess effect of EaseVRx vs. Sham VR by comparing participant Global Impression of Change (PGIC) and system usability (as measured with the System Usability Scale; SUS) at end-of-treatment for each group.	
The exploratory endpoint compares PGIC and SUS at the end of treatment across the EaseVRx and Sham groups.
 
The outcome measure used to quantify this endpoint is the PGIC and SUS survey.
	
The PGIC and SUS surveys are validated instruments with excellent content validity, construct validity, and reliability.

Exploratory Aim #6: Assess effect of EaseVRx vs. Sham VR by comparing change in all objectives from pre-treatment to end-of-treatment, 4 weeks	See descriptions above	See descriptions above

post treatment, 8 weeks post treatment, 12 weeks post treatment, 6 months post treatment, 12 months post treatment, 18 months post treatment and 24 months post treatment in the EaseVRx-8w and EaseVRx-8w plus extended on-demand groups.		
--	--	--

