14 STUDY ASSESSMENTS

14.1 EFFICACY ASSESSMENTS

Primary Outcome

The primary outcome for this study will be the BPI questionnaire. The BPI questionnaire is a validated instrument with good content validity, construct validity, and reliability in participants with chronic pain. The range of scores are from 0-10. The BPI contains a single item related to pain intensity and 7 items related to pain interference. The BPI pain interference score is the mean of seven questions that assess pain interference on general activity, mood, walking ability, normal work, relations with other people, sleep, and enjoyment of life. The higher the score the greater the impact of chronic pain on the participant.

Secondary Outcomes

Secondary outcomes include the Oswestry Disability Index score (ODI v2.1b), PROMIS Sleep Disturbance, PROMIS Depression, PROMIS Anxiety, and participant Satisfaction that will be evaluated before the intervention, immediately following the intervention (Day 56 in all arms), 4-weeks post-treatment, 8-weeks post-treatment, 12-weeks post-treatment, 6 months post-treatment, 12 months post-treatment, 18 months post-treatment, and 24 months post-treatment. participant Satisfaction will be evaluated on Day 56.

- **Oswestry Disability Index**

- The Oswestry Disability Index (also known as the Oswestry Low Back Pain Disability Questionnaire) is a tool that researchers and disability evaluators use to measure a participant's functional disability. The test is considered the 'gold standard' of low back

functional outcome tools. The *tool is well validated with excellent content validity, construct validity and reliability.*

- **PROMIS Scales Sleep Disturbance, Depression & Anxiety**

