17 STATISTICAL CONSIDERATIONS

All statistical considerations are detailed in a standalone Statistical Analysis Plan.

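### Protocol Secondary Aim #1 gives the 30% responders their own study-success rule, which the SAP contradicts; the 1- or 2-point interference threshold and the responders' adjusted or nominal status also need reconciling

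*Protocol*

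**What the plan says.** **Success rule.** The primary row of the table in Protocol Section 8 ends with "Study success will be declared if statistical significance is demonstrated on at least one of the endpoints". The row for Secondary Aim #1 (30% responders at 8 weeks) uses nearly the same words: "Interference and Intensity are tested separately, and therefore, two (2) multiplicity adjusted statistics are produced. Study success will be declared if statistical significance is", completed after a table break by the same ending. It sets no condition on the primary. The justification column of that row says "The secondary endpoint using this responder definition will accompany the primary results to help interpret the primary results" and also "The study is powered to accomplish secondary endpoints which require statistical power beyond what is required for the primary endpoint alone". Protocol Section 17 adds "All statistical considerations are detailed in a standalone Statistical Analysis Plan".

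SAP 2.3 declares success on at least one of the two primary endpoints after multiplicity correction, and names no other route. SAP 2.6 starts the responder analyses only if the primary has succeeded.

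**Point threshold.** SAP 1.3 assigns 1 point to interference and 2 points to intensity. SAP Table 1 gives 2 points for both, and the closing text of SAP 2.6 says that the stricter 2-point rule was chosen for both. Protocol Exploratory Aim #2 agrees: "Brief Pain Interference Scale (score range 0-10); CID = 2".

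**Adjusted or nominal.** For the 30% responders and for Exploratory Aims #1 and #2 the protocol says "Interference and Intensity are tested separately, and therefore, two (2) multiplicity adjusted statistics are produced". SAP 2.5 and 2.12.2 apply Hochberg only to ODI and the three PROMIS scales, and SAP 2.5 allows nominal p-values for every other endpoint. SAP 1.3 calls the 30% responders key secondary; SAP 2.6 calls them supplementary.

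**The concern.** If both primary tests failed and one responder comparison reached significance, the protocol sentence would allow success to be declared, on an analysis that the SAP would not have run. That should not be left to be argued after unblinding.

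The threshold slip matters because a 1-point rule gives different responder rates from a 2-point rule, so a report written from SAP 1.3 would not match one written from Table 1.

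The third mismatch leaves a promised adjustment with no stated family or alpha. Deferring to the SAP does not settle it, because the SAP gives the responders two different roles.

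**Working it through.** **The plan's own figure first.** With the SAP Table 2 means, SDs and correlations, 120 per group, one-sided t-tests and Hochberg at 0.025, simulation gives 97.8% power for at least one primary endpoint. This agrees with the more than 95% in SAP 2.8.1. The enrolment chain also holds: 240/0.33 = 727 (stated about 730), 730/0.85 = 859 (stated about 855), 855 + 145 = 1000. The point does not turn on sample size.

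**Size of the second route.** Inputs:
- Evaluable per pooled group: 1000 × 0.85 / 2 = 425. This assumes full enrolment and the SAP's 15% loss.
- SDs of change 1.66 (intensity) and 1.98 (interference), and correlation 0.765: midpoints of 1.64/1.68, 1.99/1.97 and 0.76/0.77 in Table 2.
- Hochberg on two p-values: success if the larger is below α or the smaller is below α/2.
- Primary test: z = difference in mean change / √(s₁²/n + s₂²/n). Responder test: z = (p₁ − p₂) / √(2p̄(1 − p̄)/n).

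Model A (40,000 trials) calls a participant a responder if the change reaches 30% of the mean baseline: 0.3 × (5.10 + 5.24)/2 = 1.55 for intensity and 0.3 × (4.78 + 5.08)/2 = 1.48 for interference. Model B (20,000 trials) draws baseline and Week 8 jointly from the Table 2 sham columns and calls a participant a responder if Week 8 is at most 0.7 × baseline. The SAP cites 5% in 2.12.1 and a one-direction test at 0.025 in 2.8.1, so both readings are shown.

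| Global null | A, two-sided 5% | B, two-sided 5% | A, one-sided 2.5% | B, one-sided 2.5% |
|---|---|---|---|---|
| Success, primary only (SAP) | 4.4% | 4.5% | 2.2% | 2.2% |
| Success by either route (protocol read literally) | 7.2% | 7.2% | 3.5% | 3.7% |

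Under model A the documents disagree (responders succeed, primary fails) in 2.8% of null trials two-sided, or 1.3% one-sided. At a quarter of the Table 2 effects this is 4.4% (4.3% in a repeat with other random draws), at half 0.5%, and at full effects 0%.

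**Interference threshold.** With normal changes from Table 2 (EaseVRx −2.56, SD 1.99; sham −1.82, SD 1.97), the responder rate at t points is Φ((|mean| − t)/SD):
- t = 1: Φ(1.56/1.99) = 78.3% against Φ(0.82/1.97) = 66.1%, a difference of 12.2 points.
- t = 2: Φ(0.56/1.99) = 61.1% against Φ(−0.18/1.97) = 46.4%, a difference of 14.7 points.

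**Adjusted or nominal.** No arithmetic applies. The protocol promises adjustment for three pairs of pain analyses: the 30% responders, the baseline-adjusted scores and the 2-point responders. None is on the list in SAP 2.5 and 2.12.2. One may be covered indirectly: SAP 2.4.1 puts baseline into the MMRM so that significance levels hold both for values and for changes. If Exploratory Aim #1 uses that model at Week 8, its p-values are those of the primary, which are already adjusted.

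**The case against.** The success sentence looks like copied text. Protocol Section 17 hands statistics to the SAP, the same row says that the responders help interpret the primary, and SAP 2.6 would not run them after a failed primary. The practical difference vanishes at the effects the trial was designed on. All of this stands, and it makes the point one of document alignment. It does not remove the conflict between a literal protocol sentence and the SAP.

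A reader might infer that the SAP makes the responders and both exploratory analyses strictly nominal. It does not: SAP 2.5 is permissive, and SAP 2.4.1 may already cover Exploratory Aim #1. Nor do the documents settle that the responders should be nominal. They are the first secondary aim and are called key secondary, and an adjusted test after primary success would fit SAP 2.6 just as well. The extra subjects in SAP 2.8.1 do not decide it, because that passage concerns 30% improvement at later time points.

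A reader might also infer that testing ODI and PROMIS without a condition on the primary breaks the error control the SAP promises. The documents do not support that. SAP 2.12.1 promises 5% only across the two primaries, SAP 2.5 and 2.12.2 set up a separate adjusted family, and those endpoints cannot make the study a success.

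**Conclusion.** Three inconsistencies stand.

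1. The protocol's success sentence for the 30% responders contradicts SAP 2.3 and 2.6. Taken literally it raises false success under the global null from about 4.5% to about 7% (two-sided 5%). These rates assume 425 evaluable per pooled group, normal changes with the Table 2 spread and correlation, and the responder models above. The disagreement is largest at small effects, about 4% of trials at a quarter of Table 2, and is 0% at full effects.
2. SAP 1.3 is the outlier on the interference threshold. The two rules give 78% against 66% and 61% against 46% responders, assuming normal changes as in Table 2.
3. The protocol's adjusted statistics for the responders and the exploratory pain analyses have no stated method in the SAP, and the responders' status is unsettled.

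None of this affects the primary test or the sample size. Whether ODI/PROMIS claims need primary success is unstated; that is a choice to make explicit and not an error.

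**What to change.** 1. Delete the success sentence from Secondary Aim #1 in Protocol Section 8. State in both documents that study success depends only on the two primary endpoints.
2. Correct SAP 1.3 to a 2-point change for both measures.
3. Give the 30% responders one status in both documents: either (a) supportive with nominal p-values, removing the adjusted-statistics wording and the key-secondary label; or (b) key secondary, tested with Hochberg across the two responder endpoints only after primary success, and added to SAP 2.12.2 with an alpha that takes account of any ODI/PROMIS claims. Align the wording of Exploratory Aims #1 and #2 in the same way, and say whether Aim #1 at Week 8 is the primary MMRM test.
4. Optional: one sentence in SAP 2.12.2 saying that ODI/PROMIS significance is claimed only within its own family and is not confirmatory if the primary fails.

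Items 1 and 2 and option (a) cost only wording. Option (b) adds an adjusted analysis and an alpha decision. The primary analysis and the sample size stay as they are.
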